# **1. Introduction**

This document gives a detailed statistical analysis plan for the trial and should be read in conjunction with the current trial protocol. Any deviations from this plan will be described in the final report or publication (see Table 1 final report template).

#### **2. Background and rationale**

The background and rationale for the trial are outlined in detail in the protocol. In brief this study test the hypothesis that weight loss through a low calorie diet can result in significant weight loss and improvement in diabetes in obese T2D patients.

#### 3. Study objectives

The principal objective is to assess the impact of a low calorie diet on weight loss in insulin-treated patients with T2D and obesity.

Secondary objectives are as follows:

• To assess the effects of low calorie diet on: body composition, diabetes control, insulin use, glucose variability, effects on appetite and hunger, beta-cell function, other diabetes medications, cardiovascular risk factors (including obstructive sleep apnoea), and quality of life.

#### 4. Study design

This is a prospective, unblinded, parallel group, randomised controlled trial. Patient participants will be identified via local GP practices, other healthcare professional and from the Diabetes Research Network. Participants will be randomised in a 1:1 ratio to Cambridge Weight Plan Group or routine care group.

#### **5. Study comparisons**

All references in this document to 'group' refer to prophylactic Cambridge Weight Plan Group or routine care group. The Cambridge Weight Plan is a diet programme commercially available in the UK and commonly used by individuals for weight loss. It is a stepped programme that includes both very low and low calorie intake stages. This study will use 800 calories as a benchmark

#### 6. Outcome measures

#### 6.1. Primary outcome(s)

The primary outcome in this study is weight loss at 12 months.

#### 6.2. Secondary outcomes

The secondary outcomes are as follows

- body composition
- diabetes control
- insulin use
- glucose variability
- other diabetes medications
- beta-cell function
- to determine effect on hunger and appetite
- cardiovascular risk factors

#### • quality of life.

# 7. Randomisation

Participants will be randomised on-line via a secure internet facility through an online software tool (Sealed Envelope Ltd). Subjects will be randomised to either to the formula low energy diet programme (LED; intervention) or gold standard clinical care (GSC; control) in a 1:1 ratio. To ensure balance of potential confounders (age, gender, ethnicity, diabetes duration) between intervention arms, minimisation method was used, allowing optimal balance in the stratifying factors. In addition a 30% chance of simple random allocation was included. Due to nature of the intervention the subjects could not be blinded.

#### 8. Sample size

To achieve a clinically significant 10 kg weight loss between groups (SD 15 kg) at a 5% significance level with 80% power, a sample size of 74 participants was required. From the literature the mean attrition rates while following a very low energy diet and low energy diet are between 0 to 52%. Accounting for approximately 20% drop out a total of 90 participants were recruitment (45 per arm).

# 9. General statistical considerations

#### 9.1. Analysis populations

All primary analyses (primary and secondary outcomes) will be by the intention to treat principle. Patients will be analysed in the treatment group to which they were randomised, and all patients shall be included whether or not they received the allocated treatment. This is to avoid any potential bias in the analysis.

#### 9.2. Handling of protocol deviations and violations

We will apply a strict definition of the intention-to-treat-principle and will consider all randomised patients in the analysis in some form regardless of deviation from the protocol. This includes patients who were randomised but later found to violate the inclusion or exclusion criteria. It does not include those participants who have specifically requested to withdraw the use of their follow-up data in the first instance; however these outcomes will be explored as per other missing responses

# **9.3. Levels of confidence and p-values**

Unless otherwise specified, estimates of differences between groups will be presented with 95%, two-sided confidence intervals. P-values will be reported from two-sided tests at the 5% significance level.

# 9.4. Adjustments for multiplicity

No correction for multiple testing will be made.

# 9.5. Interim analysis and stopping rules

Not applicable; No planned DMC or interim analysis

# 9.6. Timing of primary analysis

The primary analysis for the study will occur after the last randomised participant entered into the trial has completed 12 months follow-up.

# 9.7. Timing of other analyses

Not applicable; no longer-term analysis following the primary analysis is proposed.

# 9.8. Covariate adjustment

In the first instance, comparative estimates of differences between groups will be adjusted for the parameters listed in section 7 for the primary outcome only. Age at randomisation and duration of diabetes will be treated as a continuous variables in this adjustment. If covariate adjustment is not practical, unadjusted estimates will be produced and it will be made clear in the output why this occurred (e.g. not possible due lack of model convergence).

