#### **10.4.** Analysis methods – secondary outcomes

Secondary outcomes will be analysed using similar methods as above. Difference in the frequency of hypoglycaemic episodes between the groups was compared using mixed-effects Poisson regression with incidence rate ratio presented. Area under the curve (AUC) will be calculated using the trapezoidal rule.

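### SAP 9.8 confines adjustment for the minimisation factors to the primary outcome, while 10.4 points secondary outcomes to a model that contains them; the secondary covariate set is therefore not fixed

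*SAP*

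**What the plan says.** Four sections of the SAP bear on the point.

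- **Section 7 (Randomisation):** "To ensure balance of potential confounders (age, gender, ethnicity, diabetes duration) between intervention arms, minimisation method was used". It adds a 30% chance of simple random allocation.
- **Section 9.8 (Covariate adjustment):** in the first instance, group differences are "adjusted for the parameters listed in section 7 for the primary outcome only". It allows unadjusted estimates where adjustment proves impractical, with the reason to be reported.
- **Section 10.3 (primary outcome):** a repeated-measures mixed-model analysis of covariance. The covariates are baseline weight, the four randomisation factors, HbA1c and number of medications. Crude and adjusted estimates are both shown, and the adjusted one carries the inference.
- **Section 10.4 (secondary outcomes):** "Secondary outcomes will be analysed using similar methods as above". It names no covariates, either for the continuous outcomes or for the Poisson model for hypoglycaemic episodes.

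**The concern.** An analyst cannot tell from these sections whether the four minimisation factors belong in the secondary models. Section 9.8 reads as a general rule that keeps them out; 10.4 refers back to a model that has them in.

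An allocation method that balances on certain factors should be matched by an analysis that adjusts for them. Otherwise the model-based standard error counts variation between arms that the allocation has already largely removed, and it tends to be too large.

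The secondary outcomes in 6.2 cover nine domains, from body composition to quality of life. The trial is unblinded, and 9.4 makes no correction for multiple testing. Section 10.3 says which estimate carries the primary inference, but nothing clearly does so for the secondary outcomes. That leaves room to prefer the adjusted or the unadjusted result outcome by outcome once the data are seen.

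**Working it through.** **1. The plan's own figure.** Section 8 states "at a 5% significance level with 80% power, a sample size of 74 participants was required", for a 10 kg difference with SD 15 kg, and 9.3 specifies two-sided tests.

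- A two-sample t-test calculation with effect size 10/15 gives 36.3 per arm, rounded up to 37, or 74 in total. Power at 37 per arm is 0.808. The figure reproduces.
- Recruiting 90 with 74 evaluable means 1 − 74/90 = 17.8% dropout, in line with the stated approximate 20%.

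The point does not depend on these figures; they only show how many patients the secondary comparisons rest on.

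**2. The sections side by side.**

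| Covariate | 9.8, primary | 10.3, primary | 9.8, secondary | 10.4, secondary |
|---|---|---|---|---|
| Age, gender, ethnicity, diabetes duration | in | in | out | in, if 10.3 is followed |
| Baseline of the outcome | not mentioned | in (weight) | not mentioned | not stated |
| HbA1c, number of medications | not mentioned | in | not mentioned | not stated |

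The first row is the conflict. The second row is an omission for secondary outcomes, not an exclusion. The table also shows that 9.8 and 10.3 give different covariate lists for the primary outcome.

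**3. Size of leaving out the minimisation factors.** If the four factors jointly have multiple correlation R with the outcome, given whatever else is in the model, the unadjusted standard error is 1/√(1 − R²) times the adjusted one, ignoring degrees of freedom. The SAP gives no R. As an assumed illustration, R = 0.3 gives 1/√0.91 = 1.05, about 5% larger, and R = 0 gives no difference. With near-perfect balance on the factors, this ratio is also how far the unadjusted standard error overstates the true sampling variation. The 30% random element makes that overstatement smaller.

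**4. Size if own-baseline adjustment were also left out.** Let r be the correlation between baseline and follow-up. The SAP gives none, so the values are assumed. Relative to a follow-up-only comparison, analysis of covariance has variance 1 − r², and a change score has variance 2(1 − r).

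| r | 1 − r² | SE, follow-up only vs ANCOVA | Patients needed | 2(1 − r) | SE, change score vs ANCOVA |
|---|---|---|---|---|---|
| 0.5 | 0.75 | 1/√0.75 = 1.15 | 1/0.75 = 1.33 times | 1.0 | √(1.0/0.75) = 1.15 |
| 0.6 | 0.64 | 1/√0.64 = 1.25 | 1/0.64 = 1.56 times | 0.8 | √(0.8/0.64) = 1.12 |
| 0.7 | 0.51 | 1/√0.51 = 1.40 | 1/0.51 = 1.96 times | 0.6 | √(0.6/0.51) = 1.08 |

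In power terms, with 37 per arm, a secondary outcome with 80% power when its baseline is in the model has 76% at r = 0.3, 68% at r = 0.5 and 52% at r = 0.7 in a follow-up-only comparison. These figures describe what depends on an unstated choice. They do not describe what the plan prescribes.

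**The case against.** A reader might infer that the plan compares secondary outcomes without their own baseline values. The text does not support that. The restriction in 9.8 covers only the section 7 parameters, and a baseline outcome value is not one of them. The method that 10.4 refers to is an analysis of covariance adjusted for the baseline of the outcome analysed; carried over to another outcome, it most naturally means that outcome's own baseline. HbA1c would be a poor example in any case, since 10.3 already lists it as a covariate. The 15%, 25% and 40% figures therefore measure an omission that the plan does not call for, on assumed correlations and against a follow-up-only comparison; against a change score at r = 0.7 the loss is about 8%.

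It can also be said that 9.8 and 10.4 are compatible: secondary outcomes get a similar mixed model without the four factors. That reading is possible and would remove the contradiction. It would not remove the mismatch with the minimised allocation.

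Finally, randomisation keeps the unadjusted comparison unbiased, the standard errors err on the conservative side, only secondary outcomes are affected, and section 1 requires deviations from the plan to be reported. All of this stands and limits the severity. It does not settle which covariates the secondary models contain.

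**Conclusion.** The point holds for the minimisation factors. Section 9.8 takes them out of the secondary analyses and 10.4, by reference to 10.3, brings them in. If 9.8 is followed, the secondary analyses do not match the allocation method. Standard errors then tend to be too large by an amount that depends on how prognostic the factors are, which the SAP does not say, and that is reduced by the random element. No bias follows; the cost is precision and analyst choice.

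On own-baseline adjustment, the finding is only that it should be stated. The larger losses in the working arise only if it were in fact omitted, and they rest on assumed correlations. Severity is minor to moderate.

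**What to change.** - **9.8:** delete the words that confine adjustment to the primary outcome, and make its covariate list agree with 10.3, which adds baseline weight, HbA1c and number of medications.
- **10.4:** state that each continuous secondary outcome is analysed with the mixed-model analysis of covariance, with that outcome's own baseline value in place of baseline weight, plus the four minimisation factors.
- **10.4, continued:** say whether baseline HbA1c and baseline number of medications stay in these models. Copying the primary model unchanged would enter HbA1c twice when HbA1c is the outcome, so it should be entered once. The same applies to number of medications when that is the outcome.
- **10.4, Poisson model:** name its covariates as well, and say that the adjusted estimate carries the inference for secondary outcomes.

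The cost is a few degrees of freedom per model and a change of SAP wording. No extra data are needed beyond baseline values of the outcomes analysed.

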# 9.9. Handling missing data

In the first instance, analysis will be completed on received data only with every effort made to follow-up participants even after protocol violation to minimise any potential bias. To examine the possible impact of missing data on the results, and to make sure we are complying with the intention-to-treat principle, sensitivity analysis will be performed on the primary outcome measure. See section 10.6 for further details.

# 9.10. Distributional assumptions and outlying responses

Distributional assumptions (e.g. normality of regression residuals for continuous outcomes) will be assessed visually prior to analysis; although in the first instance the proposed primary method of estimation in this analysis plan will be followed. If responses are considered to be particularly skewed the impact of this will be examined through sensitivity analysis; this will consist of transformation of responses prior to analysis (e.g. log transformation) in the first instance. If extreme values are apparent and considered to be affecting the integrity of the analysis, sensitivity analysis consisting of removing the outlying response(s) and repeating the base analysis will be performed. Output from these analyses, if performed, will be described and presented alongside the base case analysis (or included, e.g. in appendices) with the excluded values clearly labelled.

#### 9.11. Data manipulations

The Trial Statistician will derive all responses from the raw data recorded in the database. Where data of birth is provided, age will be calculated as time from date of birth to date of randomisation.

# **10. Proposed statistical methods**

# **10.1. Study population**

A flow diagram (recommended by CONSORT) will be produced to describe the patient flow through each stage of the study.

Numbers and description of reasons (where available) will be provided at each stage, e.g. reasons withdrawing from study or why participants did not receive the allocated treatment. The following items (number of participants) will be described:

- Assessed for eligibility
- Eligible
- Randomised (by group)
- Received allocated treatment/did not receive allocated treatment (by group)
- Withdrawn/lost to follow-up (by group)
- Included in the primary analysis (by group)

# **10.2. Baseline characteristics**

Categorical data will be summarised by number of responses, frequencies and percentages. Continuous data will be summarised by the number of responses, mean and standard deviation if deemed to be normally distributed and number of responses, median and interquartile range if data appear skewed. Tests of statistical significance will not be undertaken.

# **10.3. Analysis methods – primary outcome**

The primary endpoint of weight loss at 12 months will be analysed repeated measures analysis of covariance using a mixed model to take account of the within-subject variability, using weight measurements at all post-randomisation time points and adjusting for baseline weight, randomisation factors (age, gender, ethnicity and diabetes duration), HbA1c and number of medications. The adjusted mean group differences for baseline and each time point with 95% CIs will be calculated but the primary time of interest is at 12 months. Both the crude unadjusted and adjusted estimates will be presented, but the primary inference will be based on the adjusted analysis.

#### **10.4.** Analysis methods – secondary outcomes

Secondary outcomes will be analysed using similar methods as above. Difference in the frequency of hypoglycaemic episodes between the groups was compared using mixed-effects Poisson regression with incidence rate ratio presented. Area under the curve (AUC) will be calculated using the trapezoidal rule.

# **10.5.** Analysis methods – exploratory and other outcomes

Not Applicable

#### **10.6. Sensitivity analyses**

To examine the possible impact of missing outcomes on the overall results, sensitivity analysis will be performed. This will be limited to the primary outcome measure (weight loss at 12 months) and will consist of:

- Subset of those who completed the 12 month follow-up;
- Multiple imputation by chained equation. Twenty imputed datasets will be created by replacing missing values with simulated values from a set of imputation models built from all potential prognostic and the outcome variable (weight loss). Analysis will be then be performed on each set with the results combined using Rubin's rule to obtain a single set of results (treatment effect estimate and confidence intervals);
- Last observation carried forward. i.e imputing a missing value with the last known value

# **10.7. Planned subgroup analyses**

Interpretation of subgroup analysis will be treated with caution. Analysis will be restricted to the following subgroup:

• Those in the LED group who will cease insulin usage compared to those who don't cease insulin usage

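### The only planned subgroup analysis compares insulin stoppers with non-stoppers inside the LED arm, so it is a non-randomised responder comparison that cannot estimate effect modification

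*SAP*

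**What the plan says.** SAP section 10.7 allows a single subgroup analysis ("Analysis will be restricted to the following subgroup") and defines it as "Those in the LED group who will cease insulin usage compared to those who don't cease insulin usage". The section states no outcome, no definition or time point of cessation, and no model. Its one safeguard is general: "Interpretation of subgroup analysis will be treated with caution".

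Four other parts of the SAP bear on this:

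- Section 3 describes the population as "insulin-treated patients with T2D and obesity". It also lists insulin use among the effects to be assessed ("body composition, diabetes control, insulin use, glucose variability"), and section 6.2 repeats insulin use as a secondary outcome.
- Section 2 gives the hypothesis that weight loss by low calorie diet "can result in significant weight loss and improvement in diabetes in obese T2D patients".
- Section 9.3 makes two-sided 5% p-values the default, and section 9.4 makes no correction for multiple testing.
- Section 10.5, for exploratory and other outcomes, is declared not applicable.

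**The concern.** A subgroup analysis asks whether the treatment effect differs between kinds of patient. It needs groups fixed before randomisation and a treated-versus-control comparison within each. The contrast in section 10.7 has neither. Patients enter the trial on insulin, so whether they stop is known only afterwards and may depend on how the diet went. Both groups come from the LED arm, so neither has a randomised comparator.

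The trial's own hypothesis links weight loss to improvement in diabetes. Patients who lose more weight may therefore be more likely to stop insulin. Adherence and baseline disease severity may drive both, and stopping insulin may itself affect weight. Any of these could produce a difference between stoppers and non-stoppers without any variation in the effect of the diet.

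At stake is how the result would be reported. Under its present heading and the default rules on p-values, a comparison of responders could appear as a pre-planned subgroup effect with a nominal p-value.

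**Working it through.** **Inputs from the SAP.** Section 8: difference of 10 kg, SD 15 kg, 5% significance, 80% power, 74 required, 90 recruited (45 per arm), about 20% drop-out. Section 9.3: two-sided tests.

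**Inputs assumed, because the SAP does not give them.** The outcome compared is 12-month weight loss. The share p of the LED arm that stops insulin is 0.5, varied below. The correlation ρ between weight loss and the underlying tendency to stop ranges from 0 to 0.7.

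**Step 1: the plan's own figure.** For a two-sided 5% t-test with difference 10 kg and SD 15 kg, 36 per arm gives 79.7% power and 37 per arm gives 80.8%. So 2 × 37 = 74, as stated. The 10 kg and 15 kg are consistent with the plan's sample size and are used below as the yardstick and the SD.

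**Step 2: size of the contrast.** The LED arm has 45 patients, or 45 × 0.8 = 36 after 20% drop-out, to be split into two groups.

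**Step 3: expected gap with no effect modification.** Give every LED patient the same diet effect. Let weight loss have SD 15 kg, and let a patient stop insulin when a standard normal tendency, correlated ρ with weight loss, exceeds the cut-off z that leaves a proportion p above it. Then

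expected gap = SD × ρ × [φ(z)/p + φ(z)/(1 − p)] = SD × ρ × φ(z) / [p(1 − p)].

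The common diet effect cancels. At p = 0.5, z = 0 and φ(z) = 0.3989, so φ(z)/[p(1 − p)] = 0.3989/0.25 = 1.596:

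- ρ = 0: 0 kg
- ρ = 0.1: 15 × 0.1 × 1.596 = 2.4 kg
- ρ = 0.3: 15 × 0.3 × 1.596 = 7.2 kg
- ρ = 0.5: 15 × 0.5 × 1.596 = 12.0 kg
- ρ = 0.7: 15 × 0.7 × 1.596 = 16.8 kg

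The gap equals the 10 kg design difference at ρ = 10/(15 × 1.596) = 0.42.

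**Step 4: sensitivity to the share stopping.** Expected gap in kg:

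| Share stopping | ρ = 0.1 | ρ = 0.3 | ρ = 0.5 | ρ = 0.7 |
|---|---|---|---|---|
| 25% | 2.5 | 7.6 | 12.7 | 17.8 |
| 40% or 60% | 2.4 | 7.2 | 12.1 | 16.9 |
| 50% | 2.4 | 7.2 | 12.0 | 16.8 |

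The share matters little. The correlation governs the result.

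**Step 5: how often the contrast would reach p < 0.05.** This was simulated with 20,000 trials per setting, 40% stopping, an identical effect in every patient and an unadjusted t-test:

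| ρ | 36 in the arm | 45 in the arm |
|---|---|---|
| 0 | 5.2% | 4.9% |
| 0.1 | 7.3% | 8.3% |
| 0.3 | 29.0% | 35.3% |
| 0.5 | 69.1% | 79.8% |
| 0.7 | 97.0% | 99.2% |

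At ρ = 0 the test holds its level. As ρ rises, a significant result becomes likely although no effect modification exists.

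**The case against.** The strongest reply is that section 10.7 never says what is compared. If the aim is to describe the baseline features of patients who stop insulin, reverse causation does not arise and the kilogram figures do not apply. That stands as a limit on the figures. It also shows that the section needs an outcome, a definition and a time point.

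Second, the model in section 10.3 adjusts for baseline weight, HbA1c, diabetes duration and number of medications. If section 10.7 used it, measured baseline severity would be partly handled and the gap could be smaller than an unadjusted 15 kg SD implies. This is fair, but section 10.7 does not say which model applies. Adjustment for baseline covariates would not turn a post-randomisation grouping into a baseline one.

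Third, insulin use is already a secondary outcome compared between arms, only one subgroup is planned, caution is promised, and no primary or secondary conclusion depends on it. This limits the severity. General caution still does not tell a reader that the contrast is non-randomised.

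A reader might infer that the analysis is bound to show a large difference. The SAP does not support that. It gives neither the correlation nor the share stopping, and the gap is zero at ρ = 0 and about 2.4 kg at 0.1. A reader might also infer a conflict with the intention-to-treat rule in section 9.1 ("Patients will be analysed in the treatment group to which they were randomised"). There is none: that rule governs the analyses of the primary and secondary outcomes, and a comparison within LED moves no patient out of the randomised arm.

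**Conclusion.** The structural point holds on the text alone. The only planned subgroup is defined by something that happens after randomisation, forms part of a trial outcome and is examined in one arm. It cannot estimate effect modification, and the promise of caution does not change that.

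The size is conditional. It assumes that 12-month weight loss is the outcome, that the SD within LED is 15 kg, and the threshold model above. On those terms the contrast can show anything from no gap to about 17 kg over correlations of 0 to 0.7, and it passes the "clinically significant 10 kg weight loss between groups" of section 8 at a correlation of about 0.42. The SAP does not show where in that range the trial lies.

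The primary analysis is unaffected. The section should be changed, but it does not threaten the trial's main conclusion.

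**What to change.** 1. Remove the contrast from section 10.7 and place it in section 10.5 as a descriptive table, labelled non-randomised and non-causal and without p-values. Name the outcome or outcomes shown, how cessation is defined for the analysis, and the time point at which it is assessed.
2. In section 10.4, state that inference on insulin cessation rests only on the proportion off insulin at 12 months, LED versus control as randomised. Insulin use is already a secondary outcome, so only this binary form and its method need adding.
3. Let section 10.7 state that no subgroup analysis is planned. If one is wanted, define it by a named characteristic recorded before randomisation, and test it in both arms as an exploratory treatment-by-subgroup interaction at 12 months. In the repeated-measures model this generally needs treatment-by-time-by-subgroup terms, and continuous factors such as diabetes duration need a stated form. Power would be low with 90 patients. This step is optional.

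Steps 1 and 2 cost a few lines of SAP text and one between-arm comparison, and need no new data. The descriptive information on patients who stop insulin is kept.
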